### C. Study Endpoints:

#### 1. Primary Endpoints:

- a. Central corneal thickness at day 1 postoperatively
- b. Lens removal time (from end of rhexis to complete nucleus removal)

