## 2. STUDY DESIGN AND METHODS:

A. **Test article:** Zeiss Quatera® 700 and Alcon Centurion® Vision System

B. **Study Design:** Prospective, randomized, double-masked contra lateral eye study.

C. **Subjects:** A total of 40 subjects who met the Inclusion/Exclusion criteria will be enrolled.

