#### B. Surgery Procedures:

The first eye undergoing surgery will be randomized to either the Quatera® 700 or the Centurion® Vision System. The fellow eye will receive the alternate treatment. The first operative eye will be the eye with the worse cataract. If the cataract is the same in both eyes, the clinic's standard of care will be followed. The randomization list will be provided by a third-party consultant. Research staff not attending or participating in surgery will be masked to the extent possible.

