### C. Study Visit Schedule and Assessments (Table 1).

#### 1. Visit Schedule: Subjects will be examined at the following intervals:

1. Visit 0: Screening and enrollment: Preoperative evaluation completed not more than eight weeks before surgery
2. Visit 1: Day of Surgery each eye
3. Visit 2: Day 1: (12 to 48 hours) after surgery each eye
4. Visit 3: Week 1: 7  $\pm$  2 days after surgery each eye
4. Visit 3: Month 1: 30  $\pm$  7 days postoperative after second eye surgery
4. Visit 4: Month 3: 90  $\pm$  15 days postoperative after second eye surgery

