### B. Statistical Analysis

All data will be collected by the site and entered into a database. Subjects will be assigned an ID number. Data analysis will be performed without patient identification. Statistical analysis will be performed using standard descriptive statistics and other tests as deemed appropriate based on the characteristics of the data to be analyzed. All statistical tests will be two-sided and interpreted at a 5% significance level. Comparisons between the groups will be made. Data analysis will be conducted by a third-party consultant.

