#### 2. Secondary Endpoints:

- a. Duration of surgery (from incision to wound hydration)
- b. Incision size (prior to intraocular lens implantation)
- c. Estimated fluid use
- d. Subjective signs of inflammation (cells and flare) at day 1, 7 and 30.
- e. Endothelial cell density at 3 months
- f. Central corneal thickness at day 7, 30 and 90
- g. Best corrected distance visual acuity at day 7, 30 and 90
- h. Intraocular pressure at day 1, 7, and 30
- i. Macular thickness day 7, 30 and 90
- j. Intraoperative complication rate

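### Day-1 corneal thickness and 3-month cell density are defined as raw values, and the plan pre-specifies no pairing, baseline or eye-order term

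*Combined protocol and SAP*

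**What the plan says.** - **Design.** Section 2 describes a "Prospective, randomized, double-masked contra lateral eye study". Under section 3.B (repeated in 8.B), "The first eye undergoing surgery will be randomized to either the Quatera® 700 or the Centurion® Vision System", and "The fellow eye will receive the alternate treatment".
- **Eye order.** "The first operative eye will be the eye with the worse cataract". If the two cataracts are equal, clinic practice decides.
- **Endpoints.** Section 5.C.1 gives primary (a) as "Central corneal thickness at day 1 postoperatively" and primary (b) as lens removal time. Section 5.C.2 lists "Endothelial cell density at 3 months". Neither CCT nor ECD is expressed as a change or as baseline-adjusted.
- **Baseline data.** Section 3.D and Table 1 schedule ultrasound pachymetry, Pentacam, specular microscopy and LOCS III grading at Visit 0. Both thickness instruments are used again at day 1. The endpoint does not say which one supplies CCT.
- **Analysis.** Section 5.B promises descriptive statistics, further tests chosen to suit the data, a two-sided 5% level, and "Comparisons between the groups will be made". It names no efficacy test, model, pairing or covariate, and excludes none.
- **Allocation list.** Sections 3.B and 8.C mention a third-party list and sequentially numbered envelopes. They are silent on blocking.

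**The concern.** The Introduction justifies the CCT endpoint by the change in thickness after surgery, as a marker of surgically induced oedema. A raw day-1 value also carries the natural thickness difference between a patient's two eyes, which has nothing to do with the device. That difference is measured at Visit 0 and could be removed.

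Eye order is a second known source of variation. Where the cataracts differ, the first eye is by rule the worse one, so order and severity go together within the pair. If either affects lens removal time or swelling, the within-pair device difference is raised in some patients and lowered in others, according to which device went first.

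At stake is precision in a trial of only 40 pairs. There is also some freedom of choice: raw or adjusted, with or without order, can be decided after the data are seen, for two primary endpoints each tested at 5%.

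**Working it through.** **1. The plan's own figure.** Section 5.A asks for at least 20 subjects in each of two surgical techniques: 2 × 20 = 40, the stated total. It is not a power calculation. The section says the SD is unknown, and no correlation, effect size or power is given. All SDs and correlations below are therefore assumptions.

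**2. Baseline adjustment of CCT.** Model day-1 CCT as preoperative CCT plus swelling, with swelling unrelated to the preoperative value.

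- Variance of the preoperative inter-eye difference: v0 = SD² × 2(1 − r)
- Share of paired variance removed: v0 / (v0 + s²), where s is the SD of the paired swelling difference
- Reduction in SE: 1 − sqrt(1 − share)
- Equivalent number of unadjusted pairs: 40 × (v0 + s²) / s²

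| CCT SD (µm) | r | v0 (µm²) | s (µm) | Variance removed | SE reduction | Equivalent pairs |
|---|---|---|---|---|---|---|
| 30 | 0.95 | 90 | 40 | 90/1690 = 5% | 3% | 42 |
| 35 | 0.90 | 245 | 40 | 245/1845 = 13% | 7% | 46 |
| 30 | 0.95 | 90 | 20 | 90/490 = 18% | 10% | 49 |
| 35 | 0.90 | 245 | 20 | 245/645 = 38% | 21% | 64 |

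**3. Cross-check with a different set of assumptions.** Take a per-eye between-eye SD e of 5, 8 or 12 µm, a per-eye swelling SD of 20, 40 or 60 µm, and a fellow-eye correlation of swelling c of 0, 0.3 or 0.6. The paired SE is sqrt((2e² + 2·swelling²·(1 − c))/40) for the raw value, and the same without the 2e² term for the change. At e = 8, swelling SD 40, c = 0.3 it falls from 7.7 to 7.5 µm, about 3%. In 23 of the 27 combinations the reduction is below 10%. The other four all have swelling SD 20 and e of 8 or 12. The most favourable gives 1 − sqrt(160/304) = 27%. A gain of a few per cent is the usual result.

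**4. Omitting eye order.** Let the first-minus-second-eye effect be k SDs of the paired difference. It enters the device difference with a plus or minus sign according to which device went first, so the SE is multiplied by sqrt(1 + k²):

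- k = 0.2: 1.02
- k = 0.3: 1.04
- k = 0.5: 1.12
- k = 1.0: 1.41

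**5. Uneven first-eye allocation.** If the list were simple and unblocked, the number of first eyes given one device would be Binomial(40, 0.5). The chance of a 24:16 or more uneven split is 0.27. At 24:16 the unadjusted estimate moves by (24 − 16)/40 = 0.2 of the order effect; at 20:20 it does not move. This is not additional to step 4: under an unblocked list the order term in the variance is exactly the chance imbalance. With order in the model the shift disappears, and a 24:16 split costs only sqrt(1/(4 × 24 × 16/40²)) = sqrt(1/0.96) = 1.02 in SE.

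**The case against.** The strongest reply is that section 5.B commits to no wrong analysis. Pairing is an obvious feature of data from a declared contralateral-eye study, so a paired test is fully allowed. That stands. A reader might infer that the eyes will be compared as independent groups, which would make the SE too large by 1/sqrt(1 − ρ): 1.41-fold at a fellow-eye correlation of 0.5 and 1.83-fold at 0.7. Those figures apply only if the analyst ignores pairing, and no text says so. Fisher's exact test in section 5.D does not show it either, since it is confined to the proportion of patients with adverse events.

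A reader might also infer that operating the worse eye first biases the device comparison. It does not, because the first eye's device is randomised. The rule also exempts equal cataracts, and the documents do not say that density drives swelling: the Introduction names phacoemulsification time, shorter eyes and a shallow anterior segment as risk factors for cell damage. The order effect may therefore be small, which is why the range starts at 0.2. Silence on blocking is not evidence of an unblocked list.

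The baseline gain is modest in most scenarios, and the formula treats the preoperative reading as error-free, so the real gain may be lower. It is still nearly free.

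The study is called a pilot, which limits the consequences. But section 5.B still sets significance tests at 5%, and a pilot run without a known SD should deliver the SD of the paired, adjusted difference for a later trial.

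The day-1 window ("Visit 2: Day 1: (12 to 48 hours) after surgery each eye") can differ between a patient's eyes, but no gain from adjusting for hours since surgery has been computed.

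**Conclusion.** The point holds as a gap in pre-specification with a modest, conditional cost in precision. CCT and ECD are stated as raw values although their baselines are collected, and no pairing, baseline or eye-order term is named.

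Under the assumptions in the first table, baseline adjustment of CCT saves about 5-38% of the paired variance, or 3-21% of the SE; the upper end needs the largest inter-eye differences together with the smallest swelling SD. Leaving out an order effect of 0.2-1.0 SD of the paired difference inflates the paired SE by about 2-41%. That is added variance, or a chance shift if first-eye allocation is uneven, and not bias in expectation. None of these sizes can be fixed from the documents. No separate gain was computed for ECD; the case there is the same in kind.

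**What to change.** - Define primary (a) as day-1 CCT adjusted for the same eye's preoperative CCT measured on the same instrument, and name that instrument (ultrasound pachymetry or Pentacam).
- Analyse both primary endpoints within pairs, by a mixed model with a subject effect or by regression of the within-pair difference, with device and eye order (first or second) as terms. For lens removal time there is no baseline value, so order is the only added term.
- Treat 3-month ECD in the same way, adjusted for the preoperative count.
- Ask the third party already supplying the list for permuted blocks, so that first-eye allocation is close to 20:20. Exclusions during surgery (section 2) may unbalance the analysed pairs slightly; the order term deals with that.

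LOCS III grade, a log scale for lens removal time and hours since surgery are optional. LOCS III grade overlaps with order by construction, and hours since surgery would require visit times to be logged.

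The cost is a few sentences of analysis text, a request to the consultant, and one or two degrees of freedom out of the 39 of a paired comparison of 40 subjects. No new data, visits or patients are needed.

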#### 2. Secondary Endpoints:

- a. Duration of surgery (from incision to wound hydration)
- b. Incision size (prior to intraocular lens implantation)
- c. Estimated fluid use
- d. Subjective signs of inflammation (cells and flare) at day 1, 7 and 30.
- e. Endothelial cell density at 3 months
- f. Central corneal thickness at day 7, 30 and 90
- g. Best corrected distance visual acuity at day 7, 30 and 90
- h. Intraocular pressure at day 1, 7, and 30
- i. Macular thickness day 7, 30 and 90
- j. Intraoperative complication rate

### **3. Exploratory Endpoint:**

- a. Accuracy of the Surgical Optimizer

## **D. Safety Analyses**

The type, severity, duration and frequency of reported ocular adverse events will be tabulated for each group. Adverse events will also be summarized for events that were considered treatment-related. Comparison of treatment groups with respect to the proportion of study patients reporting adverse events will be made using Fisher's Exact Test.

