### 1. Inclusion Criteria:

Subjects **MUST** fulfill the following conditions to qualify for enrollment into the trial

1. Subject is undergoing bilateral lens extraction with implantation of a posterior chamber intraocular lens.
2. Gender: Males and Females.
3. Age: 40 years or older.

4. Willing and able to provide written informed consent for participation in the study
5. Willing and able to comply with scheduled visits and other study procedures.
6. Scheduled to undergo standard cataract surgery with topical anesthesia in both eyes within 1 to 15 days between surgeries
7. Subjects requiring an IOL power in the range of +10.0 D to +30.0 D only.
8. Potential postoperative visual acuity of 0.2 logMAR (20/32 Snellen) or better in both eyes.

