### D. Measurements and evaluations

1. Visit 0: Informed consent process will be conducted at this visit. Assessments include best-corrected distance visual acuity (BCDVA, Snellen chart), manifest refraction, intraocular pressure (IOP, Goldman), corneal tomography (Pentacam), ultrasound pachymetry, specular microscopy, macular OCT, slit lamp examination including dilated fundus exam, cataract density and type (LOCS III). Any testing that is part of the site's standard of care preoperative cataract surgery evaluation may be performed prior to the informed consent being signed provided these tests are conducted within 90 days of the surgery and notation of the date performed is entered onto the CRF. The surgeon's standard pre cataract surgery treatment will be used in all his patients

First eye undergoing surgery will be randomized to Group A (Quatera 700) or B (Centurion).

2. Visit 1: The surgeon may use his preferred small incision cataract extraction technique (manual phacoemulsification or laser assisted). The same technique must be used in both eyes. The intraocular lens will be implanted in the bag. The following information will be captured the day of surgery: phaco metrics, lens removal time, duration of surgery, incision size (prior to lens implantation), estimated fluid used, lens implanted and power, target refraction for IOL power implanted, additional surgical procedures, intraoperative complications, and any device deficiencies. Additionally, the surgery will be recorded, and the videos will be analyzed digitally using the Surgery Optimizer and manually using a stopwatch. The surgeon's standard post cataract surgery treatment will be used in all patients.

3. Visit 2: monocular pinhole uncorrected visual acuity (UCVA), slit lamp examination, IOP, ultrasound pachymetry and Pentacam.
4. Visit 3: Manifest refraction, best distance corrected visual acuity (BCVA), IOP, slit lamp examination, ultrasound pachymetry, Pentacam and macular OCT.
5. Visit 4: Manifest refraction, best distance corrected visual acuity (BCVA), IOP, slit lamp examination, ultrasound pachymetry, Pentacam, macular OCT, and dilated fundus exam if deemed necessary by the investigator.
6. Visit 5: Manifest refraction, best distance corrected visual acuity (BCVA), IOP, slit lamp examination, ultrasound pachymetry, Pentacam macular OCT will be performed. Dilated fundus exam to be performed if deemed necessary by the investigator.

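### The safety section compares the two devices with Fisher's exact test, which assumes independent groups, although every patient contributes one eye to each device; a paired test should replace it

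*Combined protocol and SAP*

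**What the plan says.** Section 2.B describes the trial as a "Prospective, randomized, double-masked contra lateral eye study". The inclusion criteria require bilateral surgery: "Subject is undergoing bilateral lens extraction with implantation of a posterior chamber intraocular lens". Section 3.B (Surgery Procedures) randomizes the first eye to one of the two devices and adds: "The fellow eye will receive the alternate treatment". Section 3.D (Measurements and evaluations) fixes what a group is: "First eye undergoing surgery will be randomized to Group A (Quatera 700) or B (Centurion").

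Section 5.D (Safety Analyses) first has ocular adverse events tabulated by group. It then names the only inferential test in the plan: "Comparison of treatment groups with respect to the proportion of study patients reporting adverse events will be made using Fisher's Exact Test". Section 5.B adds "All statistical tests will be two-sided and interpreted at a 5% significance level" and otherwise leaves the choice of tests open. No paired test or within-subject model is named anywhere. The secondary endpoints include "Intraoperative complication rate", for which no test is given.

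**The concern.** Fisher's exact test compares proportions in two independent groups. Here each completed patient is in both. Applied by device, the test handles 40 matched pairs as if they were 80 unrelated units (80 is 2 × 40; the plan does not state it). The p-value then ignores whether the events on the two devices fall in the same patients or in different ones.

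The unit is also loosely worded. The sentence counts patients, but a patient who received both devices cannot be assigned to one of them; only the affected eye can. Nor does the sentence restrict itself to ocular events, and a non-ocular event cannot be attributed to a device.

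At stake is the device comparison of safety. A contralateral design is chosen to gain from the similarity of fellow eyes, and this test discards that gain. In a safety comparison, lost power pushes towards reporting no difference.

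**Working it through.** **Figure in the plan.** There is no power calculation to reproduce. The sample size, "A total of 40 subjects who met the Inclusion/Exclusion criteria will be enrolled", comes from a rule of thumb for pilot studies, and at least 20 subjects in each of two surgical techniques gives 2 × 20 = 40. The check therefore concerns the behaviour of the test.

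**Inputs from the documents.** 40 subjects, hence at most 40 pairs; two-sided 5% level; one eye per device in each subject.

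**Assumed inputs.** Event rates per eye and the between-eye correlation (phi). The documents give neither, so a range is shown.

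**Step 1: one data set, different pairings.** Suppose 14 of 40 eyes on one device and 6 of 40 on the other have an event. Let a be the number of patients with events in both eyes. The discordant counts are then b = 14 − a and c = 6 − a. Fisher uses only 14 and 6. Exact McNemar uses p = 2 × P(X ≤ min(b, c)), with X binomial(b + c, ½).

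| Both eyes (a) | Discordant b vs c | Fisher p | Exact McNemar p |
|---|---|---|---|
| 0 | 14 vs 6 | 0.069 | 0.115 |
| 3 | 11 vs 3 | 0.069 | 0.057 |
| 4 | 10 vs 2 | 0.069 | 0.039 |
| 6 | 8 vs 0 | 0.069 | 0.008 |

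For example, 10 vs 2 gives 2 × (1 + 12 + 66)/4096 = 0.039, and 8 vs 0 gives 2/256 = 0.008. For a given data set, Fisher's p-value can be too small or too large.

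**Step 2: power.** The joint probability of an event in both eyes is p11 = pA·pB + phi·√[pA(1−pA)·pB(1−pB)]. The discordant probabilities are pA − p11 and pB − p11. At 40% vs 20% with phi 0.41, p11 = 0.08 + 0.41 × 0.196 = 0.160, so the discordant probabilities are 0.240 and 0.040. Summing over every possible outcome for 40 pairs gives the probability of p ≤ 0.05:

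| Assumed rates | phi | Fisher | Exact McNemar |
|---|---|---|---|
| 40% vs 20% | 0 | 0.41 | 0.40 |
| 40% vs 20% | 0.41 | 0.38 | 0.61 |
| 40% vs 20% | 0.58 | 0.35 | 0.79 |
| 20% vs 10% | 0.3 | 0.12 | 0.18 |
| 15% vs 5% | 0 | 0.18 | 0.18 |
| 15% vs 5% | 0.3 | 0.14 | 0.20 |
| 10% vs 5% | 0.3 | 0.02 | 0.03 |

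**Step 3: no true difference.** With 25% in both groups, Fisher rejects in 0.3% of trials at phi 0.47 and in 0.02% at phi 0.69. Exact McNemar rejects in 1.9% and 0.7%. Both are below the nominal 5%, Fisher much further. With 20% in both groups and phi 0, the two are close (2.8% and 2.5%).

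**The case against.** **Could other text rescue the sentence?** Section 5.B allows further tests to suit the data, but general permission does not displace a test named for a specific comparison. Fisher would suit the femtosecond versus manual comparison in section 5.A, which is between patients. That section, however, speaks of surgical technique, whereas sections 3.B and 3.D use treatment and group for the devices.

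**Does it matter much?** This objection largely stands. The proportion with adverse events is not a listed primary, secondary or exploratory endpoint. The plan calls the study a pilot. Section 5.D also tabulates ocular events by type, severity, duration and frequency for each group, so the safety description does not rest on one p-value. At low event rates both tests usually miss a difference, and at zero correlation they perform alike.

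**Stronger readings that the documents do not support.** A reader might infer that false positives are inflated; with positively correlated eyes the error runs the other way. A reader might infer that Fisher's test is the main reason a real safety difference would be missed; at low rates the main reason is 40 pairs, and McNemar does not cure that. A reader might infer that the plan has no notion of attributing events to an eye; tabulating ocular events by device group already implies it, so this part is loose wording. Finally, the Fisher sentence does not cover the intraoperative complication rate, whose test is simply unspecified.

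**Conclusion.** The test named in section 5.D does not fit the paired design, and its p-value ignores the pairing. That follows from the documents alone. The size does not: it depends on assumed event rates and between-eye correlation. The loss is substantial if events are common and fellow eyes are clearly correlated (0.38 versus 0.61 at 40% versus 20%, phi 0.41). It is small in absolute terms if events are uncommon (0.14 versus 0.20 at 15% versus 5%, phi 0.3), and absent at zero correlation. The calculations use 40 complete pairs; there may be fewer, because subjects whose surgery is aborted in either eye are discontinued. This should be corrected before the data are analysed, but it does not threaten the primary endpoints and is not a critical defect.

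**What to change.** Replace the Fisher sentence in section 5.D with wording to this effect:

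> Ocular adverse events are attributed to the affected eye and counted per eye. Devices are compared within subject with the exact or mid-p McNemar test on discordant pairs, with a paired difference in proportions and its 95% confidence interval. Non-ocular events are listed per subject and not compared by device.

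Choose the exact or the mid-p version in advance. Apply the same paired method to the intraoperative complication rate, and say how subjects with only one operated eye are reported.

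The cost is a few lines of analysis text, with no added visits or assessments. One thing needs checking: the case report form is not among the documents, and nothing in them states that the affected eye is recorded for each adverse event. The paired visit labels in Table 1 (such as 2/2A) suggest recording by eye but do not establish it. If the form lacks that field, add it.

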All adverse events and complaints will be monitored and recorded at all study visits.

**Table 1.** Visits and Study Assessments

	Visit 0 Screening	Visit 1/1A DOS	Visit 2/2A 1-day	Visit 3/3A 1-week 7 ±2 days	Visit 4/4A 1-Month 30 ±5 days	Visit 5/5A 3-Month 90 ±15 days
Informed Consent	X					
Inclusion/Exclusion	X	X				
Demographics	X					
Past medical & ocular history	X					
Concomitant medications	X					
BCVA Snellen	X					
Pinhole uncorrected distance VA (ETDRS)			X			
Manifest refraction	X			X	X	X
Best corrected distance VA (ETDRS)				X	X	X
Intraocular Pressure (Goldman)	X		X	X	X	
Specular microscopy	X					X
Ultrasound Pachymetry	X		X	X	X	X
Pentacam	X		X	X	X	X
SLE	X		X	X	X	X

Signs of inflammation (cells and flare)	X		X	X	X	X†
Dilated fundus exam	X				X††	X††
Macular OCT	X			X	X	X
Cataract density / type (LOCS III)	X					
Phaco metrics		X				
Lens removal time		X				
Duration of surgery		X				
Incision size		X				
Surgical optimizer		X				
Estimated fluid use		X				
Adverse events	X	X	X	X	X	X

X To be performed as scheduled

† To be performed if cells and flare still present at the 1-month visit

†† To be performed as deemed necessary by the investigator.

BCVA, best corrected visual acuity

ETDRS, Early Treatment Diabetic Retinopathy Study

SLE, Slit lamp exam

OCT, Optical Coherence Tomography

LOCS, The Lens Opacities Classification System

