## 5. STATISTICAL CONSIDERATIONS

### A. Sample size

A total of 40 subjects will be enrolled. In order to calculate the sample size, we need to know an accurate estimate of the standard deviation of the outcome measure which we do not know; therefore, we consider this study a pilot trial. When estimating the sample size for a pilot study, the simplest method is to apply a sample size rule of thumb.

Browne suggests a general flat rule to 'use at least 30 subjects or greater to estimate a parameter'. However, since analysis comparing manual phaco vs. femtosecond laser assisted cataract surgery will be conducted, at least 20 subjects will be enrolled in each surgical technique (femtosecond laser/manual phaco)

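### The adverse event comparison in 5.D counts patients although every patient receives both devices, and it does not restrict events to the eye, or to the time after that eye's surgery, that would tie them to a device.

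*Combined protocol and SAP*

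**What the plan says.** - **Design.** Section 2.B describes a "Prospective, randomized, double-masked contra lateral eye study". Section 3.B randomizes the device for the first eye and adds: "The fellow eye will receive the alternate treatment". Every patient who completes both surgeries is therefore exposed to both devices.
- **Timing.** Inclusion criterion 6 requires surgery under "topical anesthesia in both eyes within 1 to 15 days between surgeries". For that interval one eye has been operated on and the other has not.
- **Recording.** Section 3.D states: "All adverse events and complaints will be monitored and recorded at all study visits". Table 1 marks adverse events from the screening visit, which section 3.C allows up to eight weeks before surgery.
- **Tabulation.** The first sentence of 5.D says that the "frequency of reported ocular adverse events will be tabulated for each group". It covers type, severity and duration as well, and is limited to ocular events. The second sentence adds a summary of treatment-related events.
- **Comparison.** The third sentence compares treatment groups "with respect to the proportion of study patients reporting adverse events", using Fisher's exact test. It names no eye, no onset window and no rule for assigning an event to a device, and it does not repeat the ocular restriction.
- **Size.** Section 5.A states: "A total of 40 subjects will be enrolled". No adverse event rate, detectable difference or power is given.

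**The concern.** This sentence is the only inferential rule for adverse events in the plan. It needs three things that it does not have: a unit that belongs to one device, a set of events that a device could have caused, and a start time after exposure.

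A systemic event, or one recorded before either surgery, belongs to neither device. If it is entered as a yes for both devices, it makes that patient's two eyes agree and hides any real difference between them, so the comparison moves toward no difference. An event in a fellow eye that has not yet been operated on is a different error. It would be charged to the device that the eye receives later.

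Without a rule, the third-party consultant who analyses the data (5.B) must choose the event set, possibly after seeing the data.

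**Working it through.** **Inputs from the documents.** 40 patients, hence 40 eyes per device if all complete both surgeries (5.A, 3.B); two-sided 5% level (5.B); Fisher's exact test (5.D).

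**Assumed inputs.** The true event rates per eye (pA, pB) and the share q of patients with an event attributable to neither eye. The two eyes' own events are taken as independent of each other and of the shared event. The documents give none of these.

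**1. The plan's own figure.** The sample size follows from the two surgical techniques in 5.A: 2 × 20 = 40. It carries no power statement, so there is no safety calculation to reproduce.

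**2. Literal reading.** If the unit is the patient and each patient has had both devices, the groups contain the same 40 people. With x patients reporting any event, the comparison is x/40 v x/40, a difference of zero whatever the devices do.

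**3. Eye-level counting with shared events entered under both devices.** The apparent rate for a device with true rate p is

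p* = p + q − pq = p(1 − q) + q

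so pA* − pB* = (1 − q)(pA − pB).

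The expected number of discordant pairs is 40(1 − q)[pA(1 − pB) + pB(1 − pA)]. For 35% v 10% and q = 0 this is 40 × (0.35 × 0.90 + 0.10 × 0.65) = 40 × 0.38 = 15.2.

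| q | Apparent rates | Difference (points) | Discordant pairs | Exact McNemar power |
|---|---|---|---|---|
| 0 | 35% v 10% | 25 | 15.2 | 69% |
| 0.1 | 41.5% v 19% | 22.5 | 13.7 | 63% |
| 0.2 | 48% v 28% | 20 | 12.2 | 56% |
| 0.3 | 54.5% v 37% | 17.5 | 10.6 | 48% |

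A paired test alone therefore does not remove the dilution.

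**4. Sensitivity to the assumed rates.** At 15% v 5%, exact McNemar power is about 18% with q = 0 and about 15% with q = 0.1. At 10% v 5% it is about 4% and 3%. At such rates the comparison says little with or without dilution.

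**5. The planned test.** At assumed rates of 5% v 30%, simulated Fisher power with paired eyes is 82% for q = 0 and falls to 57%, 33% and 19% for q = 0.1, 0.2 and 0.3. Exact McNemar on the same data falls less, from 80% to 74%, 66% and 57%.

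**6. A count example.** 2/40 v 9/40 gives Fisher p = 0.048. Entering 8 further patients, event-free in both eyes, as a yes for both devices gives 10/40 v 17/40 and p = 0.155. The device results have not changed. These 8 patients add no discordant pairs, so an exact McNemar p-value would stay the same. Under McNemar the loss comes only from patients whose eyes would otherwise have differed.

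**7. Events in an unoperated fellow eye.** If recorded by eye, such an event falls under one device, the one used later in that eye. It can create or cancel a discordant pair, depending on which device came second. The factor 1 − q and the figures above do not describe it.

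**The case against.** The strongest objection is that the plan never says stray events enter the test. A reader might infer that the comparison counts every event from screening on, systemic ones included. The documents do not support that. Table 1 governs when events are recorded, not which are compared. The first sentence of 5.D restricts the by-group tabulation to ocular events, and the comparison two sentences later can be read as testing that tabulation. A treatment-related summary is also planned, intraoperative complications are a separate secondary endpoint, and the paired visit labels in Table 1 (2/2A to 5/5A) suggest recording by eye. All of this stands, so the dilution is possible rather than established.

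Carrying over the ocular restriction still leaves the unit as the patient, sets no start at that eye's surgery, and gives no attribution rule. Taking the groups as those formed by the first eye's device (Visit 0 in 3.D labels them A and B) does not help either. The patients would then be distinct, but each would have had both devices, so the contrast would be of device order.

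A second objection is that the size rests on invented rates. That also stands: step 4 shows rates at which dilution hardly matters because power is already very low.

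A reader might also infer that the trial is set to declare the devices equally safe. The plan makes no equivalence or non-inferiority claim on safety, so that would be a misuse of the result rather than a planned conclusion.

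**Conclusion.** The point holds as a defect of specification in one sentence. The unit of comparison cannot separate the devices in this design, and the event set, onset window and attribution to a device are left open. If events attributable to neither eye are counted under both devices, the risk difference falls by exactly the factor 1 − q. The loss of power depends on rates that the documents do not give; the percentages under the working are illustrations that rest on assumed rates and independent eyes. For events in a not-yet-operated eye the error is misassignment to one device, and its size is not estimated here.

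The importance is minor to moderate. Safety is not a primary endpoint and section 5.A calls the study a pilot, but this is the only planned test of adverse events and it is easily corrected.

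**What to change.** Replace the comparison sentence of 5.D with:

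> For the device comparison, count for each eye whether it had an ocular adverse event with onset at or after the start of that eye's surgery, attributed to the device used in that eye, and compare devices within patients with a paired test (exact McNemar). Systemic events and events with onset before that eye's surgery are listed per patient and are not part of the device comparison.

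Both parts are needed: the paired test does not remove dilution, and the event restriction does not deal with the pairing that Fisher's test ignores. A confidence interval for the paired difference would be worth adding, because 40 pairs may give little power.

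The cost is the rewording, and eye and onset date on the adverse event form if they are not already there. No visits or patients are added.
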